14	1.	Lab	oratories <delete applicable="" if="" not="" section="" this=""></delete>	18
	14.1		Central and local laboratories	18
	14.2		Sample preparation and collection	18
	14.3		Laboratory procedures	18
	14.4		Sample storage and transfer	19
15	5.	Safe	ety reporting	19
16	3.	Mor	nitoring and auditing	20
17. Study committees		dy committees	20	
18. Finance and funding		ance and funding	20	
19	19. Insurance and indemnity		20	
20).	Dissemination of research findings		20
2	I References		20	

1. Glossary

AE Adverse Event

CI Chief Investigator

CRF Case Report Form

GCP Good Clinical Practice

IL- Interleukin-

JRMO Joint Research Management Office

Participant An individual who takes part in a clinical trial

PI Principal Investigator

PIS Participant Information Sheet

REC Research Ethics Committee

SAE Serious Adverse Event

SOP Standard Operating Procedure

WP Work Package

2. Signature page

CI Agreement				
The study, as detailed within this Research Protocol, will be conducted in accordance with the principles of Good Clinical Practice (GCP), the UK Policy Framework for Health and Social Care Research, and the Declaration of Helsinki and any other applicable regulations. I agree to take responsibility for the statistical analysis and oversight of this study.				
CI Name:	[name]			
Signature:	- [name]			
Date:	02/01/2024			

3. Summary and synopsis

Short title	BLYNI5	
Methodology	Laboratory-based research study using nasal tissue samples from patients with nasal polyps not on biologics (n=16), with polyps on anti-IL-5 pathway biologics (n=6) and control patients without polyposis (n=6)	
Objectives / aims	To assess the effect of IL-5 treatment/blockade on the BCR (immunoglobulin) repertoire of tissue resident airway B cells	
Number of participants	22-28 patients depending on number of patients whose samples are used in both WP1 and WP2 WP1: 10 patients WP2: 18 patients	
	Major Inclusion Criteria:	
	Patients (Aged 18 years and over) undergoing resection of nasal tissue for clinical indications (e.g. polypectomy, turbinectomy, septoplasty, tonsillectomy).	
	Able to give consent.	
Inclusion and exclusion criteria	Exclusion Criteria: Inability to give consent Previous Rituximab treatment (ever) Chemotherapy within preceding 6 months Cystic fibrosis Known current COVID infection/TB infection	
Study duration	5 years	

4. Introduction

4.1. Background

The overlapping conditions of severe asthma, nasal polyps and EGPA are all characterised by chronic eosinophilic airways inflammation. This has led to the successful development of monoclonal antibody treatments that target the primary cytokine for eosinophilic inflammation, interleukin-5 (IL-5). However the receptor for IL-5 is also expressed by other cell types and of note IL-5 was first named as a 'B cell growth factor'. Anti-IL-5 monoclonal antibody therapy may therefore have clinical action through effects on other cell types other than just eosinophils and potentially much of the beneficial effect of blocking IL-5 may be due to the effects on these other cell types. This hypothesis is supported by the excellent response of nasal polyps in clinical trials to anti-IL-5 Mepolizumab but poor clinical response to the eosinophildepleting Dexpramipexole [Laidlaw et al. 2019], and relatively weaker effect of eosinophil-depleting Benralizumab than other biologics in nasal polyp disease [Cai et al. 2022]. The expression of IL-5Ra on other cell types than just eosinophils may also influence safety considerations for Benralizumab (that targets IL-5Ra expressing cells for cell-mediated killing) as compared to biologics that block the cytokine itself. We therefore ask the question – Do IL-5 expressing B cells rather than eosinophils drive chronic rhinosinusitis with nasal polyps and associated eosinophilic airway diseases [Kariyawasam and [name], 2021]?

This is an important question as it would have an impact on the current debate over which of suppression of IL-5 (as seen with Mepolizumab) or depletion of IL-5R expressing cells (Benralizumab) is more effective and which safer – in particular depletion of IL-5R expression B cells may theoretically predispose to specific antibody deficiencies and thereby infection, or other perturbations of healthy human immunity.

Activation of B cells outside of secondary lymphoid organ germinal centres occurs in peripheral sites such as nasal polyps, under mechanisms controlled by the local peripheral tissue environment [Feldman et al. 2017]. Importantly extrafollicular B cell activation can bypass usual negative selection pressures and thereby is potentially more prone to lead to auto-antibody formation. B cells can respond to IL-5 in terms of differentiation and antibody class switching [Takatsu et al. 1998]. Plasma cells, fully differentiated B cells, in nasal polyps express IL-5Ra and respond to IL-5 [Bucheit et al. 2020]. In the MATERIAL study Mepolizumab enhanced bronchial secretory IgA production [Sabogal Pineros et al. 2019]. In contrast, IL-5Ra knock-out mice show selective immunoglobulin subclass deficiencies [Yoshida et al. 1996]. Whether IL-5 blocking and IL-5Ra depleting therapies will have the same effect on B cells is uncertain. Immunological therapies can affect B cell immunoglobulin repertoires in a manner consistent with clinical activity [[name] et al. 2012].

4.2. Rationale

This research will determine the actions of IL-5 and its blockade on tissue resident B cells in nasal polyps. Specifically, we will examine whether IL-5 contributes to class-switching, influences B cell survival and maturation, influences the expression of particular antibody subclasses.

4.3. Risks / benefits

This study will examine antibody-producing B cells in nasal tissue from patients undergoing surgery as part of their normal clinical care. The tissue samples would normally be discarded following surgery. Therefore, participation in this study does not carry additional risks. There are no direct benefits for the participants.

5. Study objectives

This is a laboratory-based study that aims to assess the effect of IL-5 treatment/blockade on the BCR (immunoglobulin) repertoire of tissue resident B cells. The primary objective is to assess the effect of IL-5 treatment / blockade on the BCR (immunoglobulin) repertoire of tissue resident airway B-cells, in particular on relative expression of different immunoglobulin classes and subclasses, in particular examining:

- (i) The relative expression across the tissue BCR repertoire of different immunoglobulin classes and subclasses in the presence/absence of IL-5 pathway blockade. The relative expression of IgE (pro-allergic), IgA (mucosal defense) and IgG4 (pro-tolerogenic in allergy but also increased in persistent nasal polyps and EGPA) immunoglobulins determines the effectiveness of antibody responses in health and disease.
 - a. We will examine whether relative expression of different immunoglobulin classes/subclasses is perturbed by IL-5 pathway blockade using BCR repertoire analysis.
 - b. We will analyse immunoglobulin VDJ hypermutation as a measure of affinity maturation of resident B cells, and whether this is affected by IL-5/blockade.
- (ii) Effects on the BCR repertoires specific to relevant target antigens in the presence/absence of IL-5 pathway blockade. B cell responses to specific pathogen antigens (e.g. Staphylococcus aureus) and auto-antigens (e.g. myeloperoxidase) are hypothesised to be of significant importance in the pathology of nasal polyps.

a. We will examine by BCR repertoire analysis the relative expression of immunoglobulin to target antigens of different classes/subclasses and whether this is perturbed by IL-5 / blockade of the IL-5 pathway.

Secondary objectives will include: Comparing BCR repertoires for convergent clonotypes evident in blood (from IDEA project) and other available BCR libraries, to assess for potential pathological clonotypes in eosinophilic airway inflammation. As single-cell sequencing will sequence both immunoglobulin heavy and light chains, in future experimental work recombinant antibodies could be generated from the sequences to further study antigenic targets of cloned antibody. If clonotypes are evident then to examine whether B cells expressing those clonotypes also express IL-5Ra and respond to IL-5.

These objectives will be studied in two work packages:

(WP1) In Vitro WP: Nasal polyp tissue from donors not on biologic therapy will be cultured with/without non-selective / target-antigen stimulation with/without recombinant IL-5 and/or blocking antibodies to IL-5 (mepolizumab in culture). BCR repertoires will be analysed by bulk RNA sequencing. Findings from BCR repertoire sequencing will be confirmed by ELISA/FACS for different antibody classes and subclasses secreted by B cell in cell culture. This WP will examine the effects of the IL-5 pathway in vitro and help optimise experiments for WP2.

(WP2) Ex Vivo WP: Nasal tissue from patients without nasal polyps, from patients with nasal polyps not on biologic therapy, and from patients with nasal polyps on biologic therapy will be analysed ex vivo for BCR repertoire by single-cell RNA sequencing. Samples from the donors for the ex-vivo WP may additionally be examined with in vitro cultures as per WP1. This WP will examine the effects of the IL-5 pathway in vivo.

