5.1. Research Questions

What are the actions of IL-5 and its blockade on tissue resident B cells in nasal polyps? Questions that follow include:

- Does IL-5 contribute to class-switching whether class of immunoglobulin secreted differs in the presence of IL-5 / blockade?
- Does IL-5 differentially contribute to survival of B cells expressing B cell receptors (immunoglobulins) of different classes and subclasses?
- Does IL-5 / blockade affect affinity maturation of B cells, necessary for optimal antibody responses to new and evolving pathogens?
- Are there clonotypes evident in nasal tissue of patients with nasal polyps selective for eosinophilic disease?

- Are there clonotypes evident in nasal tissue of BCR specific for putative auto-antigens (extending findings of current GSK-funded IDEA study that will be analysing BCR repertoires in blood from characterised patients)? - Do B cells expressing these clonotypes express IL-5Ra and respond to IL-5?

6. Study population

WP1: We will recruit the following:

Patients undergoing nasal polyp resections and tonsillectomy (n=10)

WP2: We will recruit to the following groups:

- Nasal polyps not on biologics (n=6)
- Nasal polyps on anti-IL-5(R) biologics (n=6)
- Control patients without nasal polyposis (n=6)

We will use purposive sampling in our recruitment of the nasal polyps not-on-biologics and control patients groups to attempt to match patient characteristics (i.e. asthma status, age and gender) to the patients with polyps on biologics, which is predicted to be the more difficult group to recruit. Control patients will predominantly be patients undergoing nasal surgery for deviated nasal septa (structural rather than immunological pathology).

Research tissue from a single patient may be used for both WP1 and WP2.

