13.3. Laboratory procedures

All laboratory procedures will be conducted purely for research purposes and not form part of any clinical care. Initial sample processing will be undertaken at the Blizard Laboratories, QMUL. Further pseudo-anonymised sample analyses by be undertaken by external collaborators where the assay cannot be conducted at QMUL.

Tissue samples will be dissociated by mechanical disruption. Immune cells may be isolated or enriched with magnetic beads and/or flow cytometry as per experimental protocols. Immune cells will be processed for single cell RNA sequencing using the 10X genomics platform at the genome centre core facility at the Blizard Institute. For bulk antibody repertoire analysis the tissue will be homogenized and RNA isolated from the homogenate. Antibody sequencing libraries will be generated by targeted PCR and then sequenced at the genome centre core facility at the Blizard Institute.

Subject to initial experiments being successful, B cell specificity will be interrogated using dCODE Klickmer oligonucleotide-barcoded antigens in later experiments, using antigens from viruses (e.g. covid, rhinovirus) and bacteria (e.g. Staphylococcus aureus enterotoxins [Chen et al. 2017]) known to trigger flares of nasal polyp inflammation and asthma exacerbations. dCODE oligonucleotide-barcoded putative auto-antigens,

identified as part of the ongoing GSK-funded IDEA ISS, will also be examined to compare tissue to blood B cell auto-antibody expression, and whether those B cells are IL-5 responsive.

Specific sequences will be analysed using an established computational pipeline based in the Immcantation packages (Nouri & Kleinstein. Bioinformatics 2018). Clonally-related B cell discerned by sequence identity (same VDJ gene rearrangement and CDRH3) and clonal lineages will be reconstructed. The properties of individual antibody repertoires will be analysed to quantify (per subclass) i) average clone sizes to provide a measure of clonal expansion, ii) clonal relatedness to other subclasses, and iii) frequencies of somatic hypermutation. These measures will then be compared between different patient groups (ex vivo WP) or stimulation condition (in vitro WP).

Samples may be sequenced *ex vivo* or after *in vitro* cell stimulations as described in the Study Design.

Other laboratory techniques that may be undertaken within the planned experimental work package:

- B cell flow-cytomtery
- o ELISA for immunoglobulin proteins

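### Somatic hypermutation frequency measures mutational load; by itself it cannot show affinity maturation, and in the in vitro work package it may also shift through differential cell survival

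*Protocol*

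**What the plan says.** Section 5, primary objective (i)b: "We will analyse immunoglobulin VDJ hypermutation as a measure of affinity maturation of resident B cells". The matching research question in section 5.1 is "Does IL-5 / blockade affect affinity maturation of B cells".

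Section 13.3 lists three properties to be quantified per subclass: average clone size, clonal relatedness to other subclasses, and "frequencies of somatic hypermutation". These are to be compared between patient groups in the ex vivo work package (WP2) and between stimulation conditions in the in vitro work package (WP1). The same section plans to group sequences into clones and reconstruct lineages. Antigen-barcode experiments depend on early success and address what the cells bind, not how strongly.

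Section 7 describes WP1 as isolating B cells from resected tissue, culturing them with and without stimulation, IL-5 and mepolizumab, and then sequencing the repertoire in bulk. Section 13.3 allows sequencing ex vivo or after stimulation, but does not require a pre-culture sample as a WP1 baseline.

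Section 5.1 also asks, as a separate question: "Does IL-5 differentially contribute to survival of B cells expressing B cell receptors (immunoglobulins) of different classes and subclasses".

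**The concern.** The objective ties a biological conclusion to a readout that captures half of the process. Mutation frequency counts how far sequences have moved from germline. It does not show whether the changes were selected for better binding.

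Two errors can follow. A change in mutation input, or in which mutated cells are present, could be reported as IL-5 altering affinity maturation. Conversely, a real change in selection at an unchanged mutation frequency would go unseen.

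In WP1 there is the further difficulty that the survival question and the maturation question in section 5.1 would share a readout. A difference in mean mutation frequency between culture conditions could come from either, and the measures listed in section 13.3 do not separate them.

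**Working it through.** The protocol gives no figure for this endpoint and no power calculation, so there is nothing to reproduce. The check has two parts.

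**1. What the readout can and cannot distinguish**

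| What happens | Mutation frequency per subclass | Affinity maturation |
|---|---|---|
| More mutation, selection unchanged | rises | not shown by the rise alone |
| Selection changes, mutation frequency constant | no change | changed, but missed |
| No new mutation; survival differs between subclasses only | no change, because the readout is per subclass | none |
| No new mutation; survival or expansion differs within a subclass | shifts | none |

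The second and fourth rows are the failures. The third shows that the per-subclass analysis gives real but partial protection.

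**2. How far survival alone could move a WP1 mean**

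Take one subclass holding a less mutated and a more mutated subset, with no new mutation in culture. Let f be the starting share of the more mutated subset, l and h the mutation frequencies of the two subsets, and r the survival of the more mutated subset relative to the other. Then

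mean after culture = (f·r·h + (1 − f)·l) / (f·r + 1 − f).

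All four inputs are assumptions; the protocol supplies none of them. With f = 0.5, l = 3% and h = 8%:

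- r = 1: (0.5×8 + 0.5×3) / 1 = 5.5%
- r = 1.5: (0.75×8 + 0.5×3) / 1.25 = 7.5 / 1.25 = 6.0%, a relative rise of 0.5/5.5 = 9%
- r = 2: (1.0×8 + 0.5×3) / 1.5 = 9.5 / 1.5 = 6.3%, a relative rise of 0.83/5.5 = 15%
- r = 0.5: (0.25×8 + 0.5×3) / 0.75 = 3.5 / 0.75 = 4.7%, a fall of 0.83 percentage points

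To see whether this depends on the chosen mixture, the same formula was run with l/h of 1%/6% and 2%/8% and f of 0.3, 0.5 and 0.7:

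| Relative survival r | Shift in mean (percentage points) |
|---|---|
| 0.5 | −0.6 to −1.0 |
| 1 | 0 |
| 1.5 | +0.4 to +0.6 |
| 2 | +0.6 to +1.0 |
| 3 | +0.9 to +1.6 |

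So survival within a subclass can move the mean in either direction with no mutation or selection in culture. The calculation shows that this can happen. It does not show how often, or that it would dominate.

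**The case against.** The strongest reply is that the protocol calls hypermutation a measure of maturation, not proof of it, and that section 9 describes the study as hypothesis-generating. Lineages and clone sizes are already planned, and clone size bears on expansion. The choice of a selection statistic is the kind of detail often left to a statistical analysis plan, which is not shown. Flow cytometry and ELISA after culture are planned, the survival question is openly posed, and WP1 serves partly to refine methods for WP2, where survival in culture is not at issue.

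Much of this stands, and it lowers the stakes. It does not remove the point. The link from mutation frequency to maturation is made in the primary objective itself, so an analysis plan that followed it faithfully would carry it forward. The exploratory purpose does not help if the hypothesis generated carries the wrong label. Clone size, flow cytometry and ELISA do not measure selection, and none is tied to the interpretation of hypermutation. The proxy limit applies to WP2 as well as WP1.

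Three stronger readings are tempting, and the document does not support them.

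- A reader might infer that the background contradicts the endpoint. Section 4.1 says that "extrafollicular B cell activation can bypass usual negative selection pressures and thereby is potentially more prone to lead to auto-antibody formation". That concerns negative selection and self-reactivity, and it is hedged. It does not say that selection for higher affinity is bypassed, so there is no contradiction with objective (i)b.
- A reader might infer that hypermutation data can never bear on maturation. They can, as part of a selection analysis on the planned lineages. The limit is on frequency taken alone.
- A reader might infer that WP1 hypermutation mostly reflects which cells survived. The protocol gives no culture length, survival, expansion or mutation data, so only the possibility can be stated.

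**Conclusion.** The point holds in a limited form. Section 5(i)b and section 13.3 together make per-subclass mutation frequency the stated route to a conclusion about affinity maturation, with no measure of selection or affinity beside it. Frequency alone measures mutational load and cannot by itself support that conclusion in either work package. In WP1, differential survival or expansion of already mutated cells within a subclass is an alternative explanation that the plan does not address.

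The first conclusion rests only on the text and on the definition of affinity maturation as mutation plus selection. The size of the second rests wholly on assumed values: about half a percentage point at 1.5-fold survival and up to one point at 2-fold, over the mixtures tried. This is a matter of labelling and interpretation that is worth correcting. It does not invalidate the study.

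**What to change.** - In sections 5(i)b and 13.3, describe and report mutation frequency as mutational load.
- In WP2, base any statement about affinity maturation on a selection analysis of the sequences and lineages already planned: replacement versus silent mutations in CDR and framework regions, set against an expected mutation model, with one representative sequence per clone, compared between groups.
- In WP1, interpret differences in mutation frequency between conditions as possible differential survival or expansion. Claim new mutation only where within-lineage evidence across paired conditions from the same donor supports it. A branch absent from one aliquot may simply not have been sampled, so a single such branch is weak evidence.

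The cost is some analysis time and a change of protocol wording; no further patients or tissue are needed. The drawback is precision: selection estimates will be noisy in sparse subclasses, particularly with six patients per WP2 group, and should be shown with their uncertainty.

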5.1. Research Questions

What are the actions of IL-5 and its blockade on tissue resident B cells in nasal polyps? Questions that follow include:

- Does IL-5 contribute to class-switching whether class of immunoglobulin secreted differs in the presence of IL-5 / blockade?
- Does IL-5 differentially contribute to survival of B cells expressing B cell receptors (immunoglobulins) of different classes and subclasses?
- Does IL-5 / blockade affect affinity maturation of B cells, necessary for optimal antibody responses to new and evolving pathogens?
- Are there clonotypes evident in nasal tissue of patients with nasal polyps selective for eosinophilic disease?

- Are there clonotypes evident in nasal tissue of BCR specific for putative auto-antigens (extending findings of current GSK-funded IDEA study that will be analysing BCR repertoires in blood from characterised patients)? - Do B cells expressing these clonotypes express IL-5Ra and respond to IL-5?

6. Study population

WP1: We will recruit the following:

Patients undergoing nasal polyp resections and tonsillectomy (n=10)

WP2: We will recruit to the following groups:

- Nasal polyps not on biologics (n=6)
- Nasal polyps on anti-IL-5(R) biologics (n=6)
- Control patients without nasal polyposis (n=6)

We will use purposive sampling in our recruitment of the nasal polyps not-on-biologics and control patients groups to attempt to match patient characteristics (i.e. asthma status, age and gender) to the patients with polyps on biologics, which is predicted to be the more difficult group to recruit. Control patients will predominantly be patients undergoing nasal surgery for deviated nasal septa (structural rather than immunological pathology).

Research tissue from a single patient may be used for both WP1 and WP2.

6.1. Inclusion criteria (both WP)

- Patients undergoing resection of nasal tissue for clinical indications (e.g. polypectomy, turbinectomy, septoplasty, tonsilectomy).
- Able to give consent.
- Age 18 years and over

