Nasal tissue will be collected from patients with nasal polyps not on biologics (n=6), with polyps on anti-IL-5(R) biologics (n=6) and control patients without nasal polyposis (n=6) undergoing clinically-indicated nasal surgery. Samples will be dissociated, and cells labelled with oligonucleotide-barcoded antibodies to CD20 and IL-5Ra. Single-cell B cell receptor (BCR) sequencing will be undertaken in the QMUL Core Genomics facility, and BCR repertoire (i.e. immunoglobulin repertoire) analysed to identify the immunoglobulin class, subclass and antibody sequence of tissue B cells from the three patient groups, stratified by IL-5Ra expression. Complementary bulk RNA sequencing with BCR-specific primers will be conducted to increase the depth of sequencing and enable further comparisons between groups.

These samples may additionally be examined by bulk RNA BCR sequencing after *in vitro* stimulation as per WP1. Optional collection of blood and nasoabsorption samples will be conducted at selected sites similar to WP1.

8. Study procedures

Invitation to Participate:

Invitation to Participate will be by members of the clinical team who will provide potential participants with a copy of the Participant Information Sheet (PIS) in advance of their scheduled surgery.

Patients will be identified by participating respiratory clinical teams, from those attending severe asthma services and undergoing nasal surgery as part of their comprehensive airways management, Additional patients will be identified by participating ENT teams, from those attending for surgery for nasal polyps, turbinectomy and septoplasties and reconstructive surgery.

Informed Consent Procedures and Screening:

On the day of scheduled surgery, potential participants interested in the study will be given the opportunity to ask questions from a GCP-trained member of the research team who may or may not be a member of the clinical team treating the participant. After questions have been answered potential participants will be asked to complete the written Informed Consent. Consenting participants will then be briefly screened to check they fulfil inclusion/exclusion criteria.

Data Collection (CRF):

A member of the site clinical team will complete the case report form (CRF) which contains only anonymised information but with a study code to link to patient samples (and to Consent Form for governance purposes). See Source Data section.

Sample Collection:

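### WP2 takes on-biologic tissue only from patients who reach nasal surgery while on the drug, so its comparison with untreated polyps cannot identify the in vivo effect of IL-5 blockade free of selection bias

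*Protocol*

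**What the plan says.** Section 6.1 admits to both work packages "Patients undergoing resection of nasal tissue for clinical indications" and gives polypectomy, turbinectomy, septoplasty and tonsillectomy as examples. Section 7 repeats the surgical route for the WP2 groups, ending with "control patients without nasal polyposis (n=6) undergoing clinically-indicated nasal surgery". No other source of tissue is described, and there is a single visit.

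Section 6 sets three WP2 groups of six: polyps without biologics, polyps on anti-IL-5(R) biologics, and controls without polyps. The first and third are sampled purposively, "to attempt to match patient characteristics (i.e. asthma status, age and gender) to the patients with polyps on biologics".

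Section 5 makes the effect of IL-5 treatment or blockade on the B-cell receptor repertoire the primary objective. It names IgE, IgA and IgG4 as the classes of interest, and notes that IgG4 is "also increased in persistent nasal polyps and EGPA". Of WP2 it says: "This WP will examine the effects of the IL-5 pathway in vivo".

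Section 12.2 lists, among other items, the clinical reason for surgery, biologic therapy as part of medication history, and the latest eosinophil count and FeNO. It does not list the biologic's indication, start date or duration, polyp response, or earlier polypectomies.

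**The concern.** A patient whose polyps regress enough on the drug to avoid an operation gives no tissue. Entry to the on-biologic group therefore depends on something the drug is expected to change. The protocol's own background makes this matter. Section 4.1 argues for a B-cell mechanism partly from clinical response to the drug ("This hypothesis is supported by the excellent response of nasal polyps in clinical trials to anti-IL-5 Mepolizumab"), and asks whether B cells rather than eosinophils drive the disease. If they do, the patients in whom blockade acts most strongly on B cells are the ones least likely to reach the operating theatre.

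Two misreadings are then possible. A small or absent difference between treated and untreated polyps could be taken as a sign that blockade leaves tissue B cells alone, when patients with the clearest effect were not sampled. Conversely, a higher IgG4 share in the treated group could be taken as a drug effect, when it may come from more persistent disease in that group.

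**Working it through.** **Plan figures.** The protocol gives no power calculation or effect size. Its only figures here are group sizes, and they reproduce: 10 (WP1) + 18 (WP2) = 28 without overlap. If all 6 untreated polyp patients of WP2 also serve WP1, 28 − 6 = 22.

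**The passages side by side.**
1. Route to tissue: clinically indicated surgery only (Sections 6.1 and 7), with polyps present on the drug (Section 6).
2. Timing: one visit, so no tissue from before the drug was started (Section 7).
3. Comparator: matched on three characteristics, none describing polyp persistence, earlier surgery or severity (Section 6).
4. Data: nothing listed that separates a recent starter, a patient treated for asthma and a patient whose polyps failed to respond (Section 12.2). The clinical reason for surgery helps only in part.
5. Inference: an in vivo pathway effect, with no mention of selection (Section 5).

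The WP2 contrast can be written as

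observed difference = mean effect among treated patients who reach surgery + c,

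where c is any difference in class share that arises because one group has more persistent disease. Neither term is the mean effect of blockade in treated patients, and the listed data cannot separate them.

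**Illustration of the first term. All inputs are assumed; none comes from the protocol.** Let individual effects have mean −1.0 and SD τ (in units of the between-patient SD). Let ρ be the correlation between a weak effect and residual disease, and let the fraction q with most residual disease go to surgery. For normal variables:

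mean effect among operated = −1.0 + τ × ρ × λ(q), with λ(q) = φ(z)/q, z being the upper-q point.

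λ(0.5) = 0.798, λ(0.2) = 1.400, λ(0.1) = 1.755. Example: τ = 1.0, ρ = 0.6, q = 0.2 gives −1.0 + 0.6 × 1.400 = −0.16.

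| ρ | τ = 0.5; q = 0.5 / 0.2 / 0.1 | τ = 1.0; q = 0.5 / 0.2 / 0.1 |
|---|---|---|
| −0.3 | −1.12 / −1.21 / −1.26 | −1.24 / −1.42 / −1.53 |
| 0 | −1.00 / −1.00 / −1.00 | −1.00 / −1.00 / −1.00 |
| 0.3 | −0.88 / −0.79 / −0.74 | −0.76 / −0.58 / −0.47 |
| 0.6 | −0.76 / −0.58 / −0.47 | −0.52 / −0.16 / +0.05 |
| 0.9 | −0.64 / −0.37 / −0.21 | −0.28 / +0.26 / +0.58 |

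With ρ = 0 there is no bias. With positive ρ, the direction implied if B cells drive the disease, the effect shrinks and can vanish or change sign. With negative ρ it is exaggerated. Group size does not enter the formula, so recruiting more than six per group would not remove the bias.

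**The case against.** The strongest reply is that surgery on the drug need not mean failure of the drug. Section 8 recruits through severe asthma services, so some patients may take the biologic for asthma or have started it recently. Section 6.1 admits operations other than polypectomy. This stands: enrichment is a tendency. A reader might infer that WP2 samples the patients with the least response, but no passage says so.

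Nor must a repertoire effect follow polyp response. Section 4.1 cites a drug that depletes eosinophils with poor clinical effect on polyps, and the title of that study in Section 20 reports tissue eosinophil depletion without change in polyp size. Tissue can change while the polyp stays. This is why the zero-correlation row above is a real possibility. It also rules out another tempting step, which is to set the effect to zero in non-responders and quote the resulting attenuation as a finding. That would only restate the assumption.

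On IgG4, Section 5 does not define persistent, and the untreated patients also have polyps that reached surgery. So an imbalance in persistence is possible, not shown.

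Finally, Section 9 calls the study hypothesis-generating, WP1 tests blockade in culture on tissue from donors not on biologics, and an analysis plan may exist that is not at hand. The first softens the consequence without withdrawing the aim stated for WP2. The second means that the primary objective does not rest on WP2 alone. The third does not help where the items are not collected, and eligibility, matching and source data are fixed in the protocol.

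**Conclusion.** The point holds in a limited form. The on-biologic group tends to be enriched for polyps persisting or recurring on treatment. Its comparison with untreated polyps, matched on asthma status, age and gender, cannot separate the effect of blockade from selection or from persistent disease.

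The size and direction of the bias cannot be derived from the protocol. It is absent if repertoire effect and polyp persistence are unrelated. Otherwise it depends on the strength of that link and on how few treated patients come to surgery, neither of which the protocol gives.

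A reader might go further and infer that WP2 can show nothing about blockade in vivo. The documents do not support that. WP2 still describes B cells in polyps that reach surgery during treatment, and WP1 is not affected by this selection. The change is worth making because it is cheap and bears directly on what WP2 can conclude.

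**What to change.** 1. **Section 12.2.** Add, from existing notes, the biologic's indication, start date and duration, any documented polyp response, and the number and dates of earlier polypectomies. Use the clinical reason for surgery, already collected, to mark operations for polyps persisting or recurring on the drug.
2. **Section 6.** Add earlier polypectomy (recurrent versus first surgery) to the characteristics on which matching of the untreated polyp group is attempted. This reduces confounding by persistent disease. It does not remove selection on drug failure, because untreated patients with recurrent polyps include some who would have responded.
3. **Section 5, WP2.** Restate the aim as describing B cells in polyps that come to surgery despite anti-IL-5(R) treatment, and say that a null result is not evidence that blockade has no B-cell effect.

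The cost is a few record-based CRF items, one matching characteristic and a reworded aim, with no added patients or procedures. The untreated comparator becomes somewhat harder to find, and the WP2 claim is narrower.
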